#### 4 STUDY PROCEDURES

Standard cardiac arrest data (e.g., demographics, intra- and post-arrest physiologic variables, CPR quality variables) will be collected on all subjects, extracted from the electronic medical record, continuous bedside monitors, and other patient physiologic monitoring devices (e.g., NIRS). Data elements to be collected from the pre-, intra-, and post-arrest periods include but are not limited to:

Patient Characteristics: date of birth; sex; race/ethnicity; height; weight; illness category (medical cardiac, medical non-cardiac, surgical cardiac, surgical non-cardiac, trauma). Pre-existing conditions: respiratory insufficiency; hypotension; congestive heart failure; pneumonia; sepsis; trauma; renal insufficiency; malignancy; congenital heart disease, if yes, single ventricle; if single ventricle, the anatomy is specified; if surgical palliation completed, type of most recent surgical procedure is noted (Norwood with Sano modification, Norwood with modified BT shunt, Hybrid Procedure, Bi-directional Glenn, Fontan, other); vasoactive inotropic scores (2 hours preceding CPR); pediatric cerebral performance category (PCPC) score; functional status scale (FSS) score.

CPR Event Characteristics: interventions at CPR start (e.g., vasoactive infusion); immediate cause of arrest (Y/N for hypotension, respiratory decompensation, arrhythmia, cyanosis without respiratory decompensation); first documented rhythm requiring CPR; time of first shockable rhythm; pre-shock pause (seconds); time of first defibrillation; time of first vasopressor administration for non-shockable rhythm; drug interventions during CPR; duration of CPR (minutes). CPR mechanics variables: Compression depth (mm); rate (per minute); chest compression fraction; and leaning during relaxation phase (release velocity, if available [mm/second]). Ventilation variables: ETCO2 (mmHg); ventilation rate (bpm); airway opening index; other ventilation variables as available (e.g., Peak Inspiratory Pressure [cmH2O]). Intra-arrest physiology (arterial BP (mmHg), ETCO2 (mmHg), and arterial/venous blood gases.

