#### 6.3 Statistical Methods

[figure not shown]
For analysis, each CPR event will be divided into multiple 30-second epochs. An average of the following will be calculated: 1) ventilation rate (bpm); 2) ETCO2 (mmHg); 3) compression rate; 4) arterial BPs; 5) chest compression fraction; 6) compression depth (mm); 7) exhaled tidal volume (mL); 8) minute ventilation (L/minute); 9) PIP (cm H2O); 10) PEEP (cm H2O); 11) % leak; and 12) cerebral oxygen saturation. An average of all epochs (event-level average) will be used in survival analyses.

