#### Primary Objective (Efficacy of OPTI-VENT bundle)

The analysis of our primary outcome is based on all enrolled index events (first in-ICU cardiac arrest) excluding transition periods. For the primary analysis of the interventional trial, a mixed effect logistic regression model will be fit with our primary outcome as the dependent variable. The primary predictor will be treatment group, an indicator of whether the *OPTI-VENT* bundle was fully implemented prior to the arrest. Fixed covariates will be illness category, age, first documented rhythm, and time since trial start (to prevent confounding due to unrelated temporal changes in outcome). Etiology and severity of pre-existing lung disease will be evaluated as a confounder / effect modifier. Unit will be included as a random effect to account for heterogeneity in patient outcomes across ICUs and to accommodate clustering of patients within ICUs. The null hypothesis will be tested using the standard type III test for the fixed effect, and the p-value for the two-sided alternative will be presented.

Brief Description of Secondary Analytic Objectives

Ventilation Rate and Survival: We will explore the relationship between ventilation rate and survival using cubic splines and ROC curves. We will randomly divide our cohort into a derivation set (70%) and a validation set (30%). The derivation set will be used in an exploratory fashion to identify an optimal target using cubic splines and ROC curves in conjunction with clinical expertise. Then, the validation set will be used to validate the rate selected and to provide an unbiased estimate of the effect of achieving the target rate on outcome. Cubic splines will allow us to create a smooth curve of survival probability on the vertical axis against the event-level average ventilation rate on the horizontal axis, while controlling for potential confounders. We plan to stratify our analysis by age,

**Figure 2:** Airway Opening Index. The sum of the delta in ETCO2 divided by the max ETCO2 caused by each chest compression is averaged by the number of CCs. Higher values indicate greater airway patency.

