and either adjust for / stratify by initial rhythm, immediate cause of arrest (e.g., respiratory deterioration, shock, sudden arrhythmia), severity (none, non-severe, severe) and etiology (none, obstructive, restrictive, mixed) of pre-existing lung disease, chest compression depth and rate (AHA compliant vs. not), and clinical site. If an alternative ventilation rate target is identified, we will quantify its association with survival outcomes using logistic regression models. Similarly, we will also explore the relationship between ventilation rate and 1) arterial diastolic BP and 2) exhaled carbon dioxide using linear regression models. For this analysis, individual epoch data will be used. Models will be adjusted for the same variables as above and account for the clustering of epochs from within events.

Evaluation of Airway Opening Index: The calculation of Airway Opening Index will be done in the manner as described in Grieco et.al. (Figure 2). As with other variables, an average AOI for each 30-second CPR epoch will be calculated. For each event, the average of all the epochs will be calculated to be used in logistic regression survival analyses. Epoch-level data will be used in a similar fashion as described above to evaluate the association of AOI with intra-arrest physiology (e.g., blood pressure and ETCO2) and delivered airway pressures (e.g., positive end expiratory pressure) in linear regression models, accounting for the clustering of epochs from within events. In addition to these standard statistical methods, this exploratory aim will involve the development of a multi-modal ML model. The input data will comprise both discrete values (e.g., demographic and clinical variables, ETCO2, I/E ratio) and high-fidelity waveform data (e.g., arterial BP, capnogram). To evaluate model performance, we will use metrics such as accuracy, F1-score, and AUC-ROC.

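### The 30% validation set will not give an unbiased effect of ventilation rate: the split leaves confounding in place, and the whole-event average can carry CPR duration

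*Protocol*

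**What the plan says.** The passage is the ventilation-rate and survival paragraph of Protocol 6.3, a secondary objective. A target rate is chosen in a 70% derivation set using cubic splines and ROC curves. The remaining 30% is then used to validate the chosen rate and "to provide an unbiased estimate of the effect of achieving the target rate on outcome".

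The exposure is fixed at the start of 6.3: "An average of all epochs (event-level average) will be used in survival analyses". The spline analysis repeats it, plotting survival "against the event-level average ventilation rate on the horizontal axis, while controlling for potential confounders".

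The named factors are age ("We plan to stratify our analysis by age"), then "and either adjust for / stratify by initial rhythm, immediate cause of arrest", then severity and etiology "of pre-existing lung disease, chest compression depth and rate (AHA compliant vs. not), and clinical site". CPR duration is not named, although Section 4 lists it, in minutes, among the event data. No early window or landmark is given for the exposure.

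Elsewhere the protocol is more cautious. Section 2.1 describes the secondary objectives as observational studies embedded in the trial, and 6.3 later speaks of the association of an alternative target with survival.

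**The concern.** Two separate issues meet in one sentence.

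First, the property claimed for the validation set does not follow from the split. Random division protects against over-fitting the cut-off. It does nothing about the reasons why some arrests are ventilated at the target rate and others are not.

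Second, the exposure is measured over a period that ends when CPR ends. A one-minute arrest contributes two 30-second epochs and a thirty-minute arrest contributes sixty. Being at target can therefore partly reflect duration, and CPR ends either when circulation returns or when efforts stop. A bias arising this way would recur in the validation set, so a target could appear confirmed, or be missed, for reasons unrelated to ventilation. Section 9.4.3 expects the findings to inform future guidelines, so the strength of the claim matters.

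**Working it through.** **The plan's own figure.** 6.4 gives about 360 index events a year, less about 7 in transition: (360 − 7) × 4.25 ≈ 1,500. With 20% unusable, 1,500 × 0.8 = 1,200. For 30% against 40% survival with half at target (600 per group, two-sided alpha 0.05 assumed for this calculation):

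- null SE = √(0.35 × 0.65 × 2/600) = 0.02754
- alternative SE = √((0.21 + 0.24)/600) = 0.02739
- z = (0.10 − 1.96 × 0.02754)/0.02739 = 1.68, power 95.4%

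With 40% or 60% at target the power is 94.6%. The stated figure of more than 90% reproduces and is not in dispute. The planned effect is an odds ratio of (0.40/0.60)/(0.30/0.70) = 1.56. The validation set holds about 1,200 × 0.30 = 360 children.

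**How duration enters the average.** The documents give no within-event drift of the rate, no duration distribution and no duration–survival relation. Everything below rests on assumptions: starting rate 25 bpm, between-event SD 6, epoch SD 8, target 20–30 bpm. For k epochs, the mean is 25 + drift × mean elapsed time and the variance is 36 + 64/k. Drift stops after 20 minutes.

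| CPR duration | k | SD of average | At target, no drift | Mean rate, drift +1 bpm/min | At target, drift +1 bpm/min |
|---|---|---|---|---|---|
| 1 min | 2 | √68 = 8.25 | 46% | 25.25 | 46% |
| 8 min | 16 | √40 = 6.32 | 57% | 28.75 | 50% |
| 30 min | 60 | √37.07 = 6.09 | 59% | 38.17 | 9% |

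Without drift, short events are at target somewhat less often because their averages are noisier. With drift, long events leave the target.

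**What this does to the odds ratio when rate has no effect.** Two sets of simulations were run.

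*Steady drift.* Log-normal duration with median 8 min, range 1–90. The survival log-odds are −1 − β(ln duration − ln 8), with β 0.5 or 0.8, giving overall survival of 28–29%. There were 400 replicates per scenario. Odds ratios are for N = 360:

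- no drift: 0.92–0.95
- 0.25 bpm/min: 0.97–1.02
- ±0.5 bpm/min: 1.06–1.13
- 1 bpm/min: 1.29–1.44 (risk difference 5–8 points), with false-positive rates of 19–36% at N = 360 and 48–79% at N = 1,200
- log duration added to the model: false-positive rate 3–7% in every scenario
- average over the first 5 minutes, drift 0.5: 0.94–0.98 (N = 360 and 1,200), not exactly 1 because shorter events still have fewer epochs

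*Early excess that decays.* Median duration 7 min, range 1–60, log-odds 0.6 − 0.55 ln duration, time constant 5 min, mean rates of 20–30 bpm. SD 10 and within-subject correlation 0.60 are borrowed from the blood-pressure power calculation in 6.4:

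- no drift: 0.97–0.99
- 4 bpm: 0.93–1.02
- 8–12 bpm: 0.81–1.01

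This model implies about 39% survival, above the plan's 30%.

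These are not outer limits. An abrupt step to 25 bpm after 1–4 minutes, from a start of 14 or 32–40 bpm, gave 0.60–0.88.

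**The case against.** *The word is meant narrowly.* It sits in the sentence about derivation and validation, where freedom from cut-off optimism is the natural sense, and the protocol elsewhere says association and promises control of confounders. This is a fair account of intent. It does not rescue the sentence as written, which claims an unbiased effect on outcome.

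*Covariates can be left to the statistical analysis plan.* This largely stands. The section is only a brief description, and its general phrase on confounders leaves room for duration. What is not left open is the whole-event average and the stated property of the estimate.

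*Leaving duration out is not in itself an error.* This stands. Duration is settled after ventilation begins and may lie on the path from rate to earlier return of circulation to survival. Adjusting for it could remove part of a real effect.

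*An early window has its own problems.* This stands. One minute of CPR is enough for eligibility, so a two-minute window is not common to all events. An airway may be placed up to five minutes into CPR, so early rates may be missing or reflect another mode of ventilation.

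A reader might go further and infer that the analysis is biased by a known amount or in a known direction, or that an early window must replace the main exposure. The documents support neither. They supply none of the inputs that determine the bias, and plausible inputs put the odds ratio on either side of 1. Nor does the point reach the primary result: that analysis compares bundle implementation, not measured rate.

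**Conclusion.** The point holds as a correction of a stated property. The random split does not make the estimate unbiased, and this needs no simulation. The duration mechanism is a specific route by which the whole-event average could mislead. It is small if rates are stable within an event: odds ratio about 0.92 to 0.99 under no true effect. With marked gradual drift it can be material, about 0.8 to 1.4 against a planned effect of 1.56, and an abrupt change could push it further from 1. Size and direction depend entirely on the assumed drift and the assumed link between duration and survival. The change is advisable but not critical, because the objective is secondary and observational.

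**What to change.** 1. In 6.3, replace the claim with: *an estimate of the adjusted association, free of selection optimism*.
2. Prespecify a sensitivity analysis in which duration cannot drive the exposure, such as the rate over an early window or a landmark analysis. State the rule for events shorter than the window and for airways placed after CPR starts.
3. Report a duration-adjusted model beside it, noting that duration may lie on the causal path.
4. Interpret a target as validated only if it is consistent across these analyses.

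The whole-event average can remain the main exposure; replacing it would be a trade-off. The 30-second epochs and CPR duration are already collected, so no new data are needed. The cost is a little more analysis and a weaker claim.

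### The observational ventilation-rate analyses name their adjustment variables but leave out illness category, so cardiac and surgical case mix can remain in the selected rate and its estimate

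*Protocol*

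**What the plan says.** The protocol's Section 6.3 describes two kinds of analysis.

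- **Randomised comparison of the bundle.** The mixed logistic model is specified as follows: "Fixed covariates will be illness category, age, first documented rhythm, and time since trial start". Unit is a random effect.
- **Ventilation rate and survival.** Section 2.1 places this among the embedded observational studies. The spline curve is to be fitted "while controlling for potential confounders", and the variables are then named. Age is the stratifier. Rhythm and the trigger of the arrest come next, as variables for adjustment or strata: "and either adjust for / stratify by initial rhythm, immediate cause of arrest (e.g., respiratory deterioration, shock, sudden arrhythmia"). After these the protocol names how severe any earlier lung disease was and of what type, each with its levels. The list ends with "chest compression depth and rate (AHA compliant vs. not), and clinical site".

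For the epoch-level models of diastolic pressure and exhaled CO2, the section says: "Models will be adjusted for the same variables as above and account for the clustering of epochs from within events".

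Illness category is not in the second list. Section 4 collects it on all subjects: "illness category (medical cardiac, medical non-cardiac, surgical cardiac, surgical non-cardiac, trauma").

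The cohort is split at random, 70% to choose a rate and 30% to validate it. Section 6.3 describes the validation-set result as an unbiased estimate of the effect of reaching the target rate.

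**The concern.** Randomisation protects the bundle comparison against case mix, and that model adjusts for illness category anyway. The ventilation-rate analysis has no such protection and depends wholly on adjustment, yet its list lacks the variable.

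Medical cardiac, surgical cardiac, non-cardiac and trauma patients may plausibly differ both in outcome and in how they are ventilated during CPR. If they do, the fitted curve partly describes which children were ventilated at each rate, and the chosen rate inherits that.

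The hold-out sample does not reveal the problem. A random split guards against optimism from choosing the rate on the same data. Both parts share the same case mix, so both carry the same confounding. What is at stake is a secondary objective, the search for an alternative rate; Section 9.4.3 expects the trial's findings to reach future guidelines.

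**Working it through.** **1. The two lists side by side**

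| Variable | Randomised primary model | Ventilation-rate analyses |
|---|---|---|
| Illness category | yes | **not listed** |
| Age | yes | yes (stratifier) |
| First/initial rhythm | yes | yes |
| Immediate cause of arrest | no | yes |
| Lung-disease severity and etiology | to be evaluated | yes |
| Compression depth and rate | no | yes |
| Site or unit | random effect | yes (site) |

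Immediate cause, as Section 4 defines it, describes the trigger: hypotension, respiratory decompensation, arrhythmia, or cyanosis without respiratory decompensation. A surgical cardiac child and a medical non-cardiac child can share trigger, rhythm, age and site. No listed variable separates cardiac from non-cardiac or surgical from medical patients.

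**2. The plan's own power figures reproduce**

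Inputs from Section 6.4: about 1200 subjects, 30% versus 40%, 40% to 60% at target. A two-sided alpha of 0.05 is stated there only for the blood-pressure calculation and is assumed here. The method is the pooled normal approximation.

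With half at target (600 per group):
- SE under the null = sqrt(2 × 0.35 × 0.65 / 600) = 0.02754
- SE under the alternative = sqrt((0.21 + 0.24) / 600) = 0.02739
- z = (0.10 − 1.96 × 0.02754) / 0.02739 = 1.68, so power is 95.4%

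At 40% or 60% at target it is 94.6%. For 350 subjects and 30% versus 45% it is 81% to 83%. The stated figures of more than 90% and more than 80% hold. Neither calculation allows for confounding.

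**3. Illustration of the confounding**

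The protocol gives no outcome or at-target share by illness category, so every input below is an assumption. There is no true effect of rate and no other adjustment.

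| Group | Share | Favourable outcome | At target |
|---|---|---|---|
| A | 40% | 22% | 40% |
| B | 25% | 25% | 45% |
| C | 35% | 42% | 60% |

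Overall outcome = 0.088 + 0.0625 + 0.147 = 29.75%, close to the plan's 30%.

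- At target: (0.160 × 0.22 + 0.1125 × 0.25 + 0.210 × 0.42) / 0.4825 = 0.1515 / 0.4825 = 31.4%
- Off target: (0.240 × 0.22 + 0.1375 × 0.25 + 0.140 × 0.42) / 0.5175 = 0.1460 / 0.5175 = 28.2%
- Spurious difference d = 3.2 points

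Rejection rate = P(|Z + d/SE| > 1.96), with SE = sqrt(0.21 × 4 / N), half at target:

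- N = 1200: SE = 0.0265, d/SE = 1.21, rejection about 23%
- N = 0.30 × 1200 = 360: SE = 0.0483, d/SE = 0.66, rejection about 10%

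The nominal rate is 5%. The second line matches the planned estimate, since Section 6.3 takes it from the validation set. The bias in points is the same in both.

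**4. How it moves with the assumptions**

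With two groups, the spurious difference is D × g. D is the outcome difference between the groups. g is the difference in one group's share between at-target and off-target events.

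- D = 10 points, g = 0.10: 1.0 point (odds ratio 1.05)
- D = 20 points, g = 0.20: 4.0 points (odds ratio 1.21)
- D = 25 points, g = 0.30: 7.5 points (odds ratio 1.43)

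These are values at chosen inputs. They are neither limits nor estimates of what the trial will show.

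**The case against.** The strongest reply is that this is material for the statistical analysis plan. The text stands under a heading that calls itself a brief description, its language is exploratory, and it commits in general terms to controlling for confounders. Nothing calls the list exclusive. This carries some weight: the analysis plan could add the variable. But the protocol does not defer the choice. It names the variables without any word such as including, and reuses them in further models. The general phrase names none.

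Secondly, the two analyses have different exposures and need not share covariates, and the ventilation-rate list is the longer one. That is correct, so this is not a contradiction between passages. It is a gap in a list that has to carry the whole burden of confounding control. Immediate cause, rhythm, age and site overlap with illness category, so the residual bias is probably smaller than the unadjusted illustration. How much smaller cannot be worked out from the protocol.

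Thirdly, illness category is constant within an event and cannot confound the within-event part of the pressure and CO2 associations. That stands. The between-event part remains exposed, and no size is given for it here.

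A reader might also infer that the airway opening index models share the omission, because their epoch data are to be used in a similar way. The protocol does not clearly state a covariate list for them, so that is not supported.

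**Conclusion.** The omission is real, and it concerns the rate-survival, rate-diastolic-pressure and rate-exhaled-CO2 analyses. Residual confounding by cardiac and surgical case mix can enter the selected rate and its validation-set estimate, so calling that estimate unbiased is not justified by the random split.

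Size and direction are unknown. The figure of about 3 points, with a false-positive rate of about 10% in 360 subjects or 23% in 1200, rests on an assumed case mix and on no other adjustment. A reader might take such figures as the expected error, or as an upper bound on it. The protocol supports neither: other inputs give larger or smaller values, and partial adjustment need not always shrink bias.

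This is worth correcting because the variable is already collected and the change is small. It concerns a secondary objective. The randomised primary analysis is unaffected.

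**What to change.** In Section 6.3, add illness category, with the five levels of Section 4 and sparse levels combined if needed, to the list for the rate-survival, rate-diastolic-pressure and rate-exhaled-CO2 models. Describe the validation-set result as an adjusted association, not as an unbiased estimate of the effect. Do both before the rate is selected, so that the addition cannot look data-driven. The airway opening index models could use the same list if the sponsor wishes; the protocol would then need to say so.

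No new data are needed. The cost is one phrase, one rewording and up to four degrees of freedom (five levels less one). That is minor with about 1200 subjects. It matters somewhat more in the validation set (about 360 subjects, or some 108 survivors at 30%) and in the diastolic pressure model (about 300 subjects), which is the reason to allow sparse levels to be combined.

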## 1.2 Name and Description of Investigational Product or Intervention

The *OPTI-VENT* bundle consists of two main components: 1) provider education: physician, registered nurse, and respiratory therapist education (via scheduled existing educational or quality meetings) and 2) point-of-care ventilation guidance (CPR cue cards highlighting ventilation rate targets and the introduction of a ventilation rate metronome). The primary ventilation training targets will be: 30 breaths per minute (bpm) for infants < 1 year of age (1 breath every 2 seconds) and 20 bpm for older children (1 breath every 3 seconds), consistent with 2020 AHA Guidelines (5).

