# 1.3 Findings from Non-Clinical and Clinical Studies

#### 1.3.1.1 Clinical Studies in Children

- In a previous NHLBI-funded multicenter study (6), we evaluated the association between CPR ventilation rates and survival. In this study of 47 intubated children who suffered a cardiac arrest, "high ventilation rates," defined as ≥30 bpm among infants <1 year of age and ≥25 bpm among older children, were associated with a more than 4x greater likelihood of survival to hospital discharge with favorable neurologic outcome (primary outcome of this investigation). Our data were translated by the AHA CPR Guideline committee into a target rate of 20 − 30 bpm.
- The *OPTI-VENT* bundle provider education in our pilot work followed a "low-intensity / high frequency" (spaced learning) training paradigm. Our team has pioneered this approach (7), documenting its effectiveness to improve compression quality. In a single-center study, the *OPTI-VENT* bundle improved ventilation rate target compliance (absolute risk reduction of ventilation rates exceeding 30 bpm: 22%, [CI95 16% 28%], p<0.001) (8).
- A recent landmark study established that intrathoracic airway closure impacts CPR ventilation (9). In this 3-part series of investigations, end-tidal carbon dioxide (ETCO2) waveforms waveforms that are part of standard clinical care in ventilated patients in ICUs were used to infer the degree of airway closure during CPR. Importantly, the degree of airway closure could be mitigated, and the ventilation during CPR improved, by small increases in the amount of airway pressure delivered during CPR. By maintaining airway patency, the chest compression oscillations provide a tidal volume (i.e., size of the delivered breath) that is additive to the tidal volume provided by the rescuer during CPR.

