#### Secondary Analytic Objectives

Ventilation Rate and Survival: We conservatively estimate that ~20% of our subjects will not have usable ventilation data. Given the remaining cohort (~1200 patients), we will have more than 90% power to detect an improvement in survival from 30% to 40% if the ventilation rate is at target in 40%-60% of subjects. Given the absolute change in survival associated with the ventilation target from our preliminary data was >20%, we are conservatively powered for the primary objective of this aim. In subgroups as small as 350, we will have >80% power to detect an improvement in survival probability from 30% to 45%. Additionally, our preliminary data demonstrate that >25% of our patients with usable ventilation data will also have usable arterial BP data. With 300 subjects, we have >80% power to detect an association between ventilation rate and diastolic BP (assumptions: standard deviation of 10 mmHg for both; slope of line -2.10 mmHg / 10 bpm; ≥seven 30-second epochs of data per subject; within subject correlation of 0.60; two-sided alpha = 0.05).

Airway Opening Index: As this objective is exploratory in nature, a power calculation is not provided.

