#### 7 STUDY INTERVENTION

## 7.1 Description

**Description of the Resuscitation Bundle:** The *OPTI-VENT* QI bundle consists of two main components: 1) provider education: physician, registered nurse, and respiratory therapist education (via scheduled existing educational or quality meetings) and 2) point-of-care ventilation guidance (CPR cue cards highlighting ventilation rate targets and introduction of a ventilation rate metronome [Figure 3]).

Provider Education / Point-of-Care Guidance: Point-of-care training will be conducted by pediRES-Q network site quality physician champions, leveraging their experience with high-risk patient identification. In short, many of these network sites are already completing bedside preparation for cardiac arrest resuscitation in high-risk patients (18). During this brief (<2 minute) bedside education, the educator will 1) review the CPR ventilation rate target, and 2) ensure the provider has

their rate cue card on his/her person and knows how to activate the CPR ventilation rate metronome

**Figure 3:** Ventilation rate metronome on CHOP's CPR Monitoring Cart (standard clinical practice).

(Figure 3). Compliance will be defined as performance of at least 30 of these trainings per unit per month (~1 per day). Although our application focuses on ventilation rate, current Guidelines recommend that inflation pressures be targeted to "visible chest rise," without prescribing an actual peak inflating or end expiratory pressure. In an attempt to standardize this portion of care, we will leverage these two-minute trainings to review the patient's current ventilator settings as a starting point during CPR to ensure adequate chest rise. Post-arrest care ventilation and oxygenation goals (e.g., avoidance of hypocarbia) will also be reviewed. Additionally, an educational focus on CPR ventilation rates will be integrated into existing resuscitation education or quality meetings across all disciplines. A brief Microsoft PowerPoint presentation focusing on the benefits of CPR ventilation rate compliance will be developed and standardized for distribution across all sites. Past performance during actual cardiac arrests will also be presented to providers during the existing cardiac arrest debriefing programs that occur in all sites participating in this trial. To be compliant with this portion of the intervention, this must occur monthly. "Report cards" detailing unit-level performance will

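### The pooled ventilation-rate analyses adjust for site but not for time since trial start (or, as a sensitivity check, bundle status), so the validation estimate cannot be called unbiased

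*Protocol*

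**What the plan says.** **Adjustment set.** Protocol 6.3, under Ventilation Rate and Survival, stratifies by age. It adjusts for or stratifies by initial rhythm, immediate cause of arrest, severity and etiology of lung disease, and "chest compression depth and rate (AHA compliant vs. not), and clinical site". The epoch-level models of rate against diastolic pressure and exhaled CO2 reuse the same variables. Time since trial start and bundle status are not listed. The primary model in the same section has treatment group as its predictor and time since trial start as a covariate, the latter expressly to guard against temporal confounding.

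**Cohort.** The rate analysis splits the cohort at random 70/30 and says the validation part gives an unbiased estimate of the effect of reaching the target rate. Section 6.4 sizes it on the pooled cohort: "Given the remaining cohort (~1200 patients), we will have more than 90% power".

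**Bundle content.** Section 1.2 says "The *OPTI-VENT* bundle consists of two main components", namely education and rate guidance. Section 7.1 opens in the same way and then adds to the bedside sessions: "we will leverage these two-minute trainings to review the patient's current ventilator settings as a starting point during CPR to ensure adequate chest rise". It continues: "Post-arrest care ventilation and oxygenation goals (e.g., avoidance of hypocarbia) will also be reviewed".

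**Design.** Under section 3.2, 5 sites are always control, 5 are always intervention, and 10 start in control and cross over at random times.

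**The concern.** The bundle is meant to be the main determinant of ventilation rate: section 6.4 assumes 20% on target in control and 85% to 95% under the bundle. In a pooled cohort, on-target events are therefore mostly bundle events and, at the stepped sites, mostly later events. Whatever else differs between early and late, or between control and bundle, can be read as an effect of rate.

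A random split guards against optimism from choosing the target rate and estimating its effect in the same data. It does not guard against confounding, because both parts hold the same mix of phases and calendar periods.

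The protocol intends its findings to inform guideline ventilation targets (section 9.4.3), so a biased estimate presented as unbiased would matter.

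**Working it through.** **1. The plan's own figures, and that the cohort is pooled.** Section 6.4 gives about 360 index events a year, about 7 lost to transition, and 20% without usable ventilation data.
- (360 − 7) × 4.25 = 1,500; 0.8 × 1,500 = 1,200.
- Two-proportion power, N = 1,200, 30% vs 40%, two-sided alpha 0.05 (assumed for this calculation): 94.6%, 95.4% and 94.6% with 40%, 50% and 60% on target. The stated figure of more than 90% reproduces.
- Pooled on-target share with equal groups: 0.5 × 0.20 + 0.5 × 0.85 = 52.5%, up to 0.5 × 0.20 + 0.5 × 0.95 = 57.5%. This lies inside the stated 40% to 60%. Both this and the 1,200 fit an analysis of both groups together.

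**2. Link between rate and bundle, unadjusted** (90% vs 20% compliance, half of events under the bundle).
- P(bundle | on target) = 0.45 / (0.45 + 0.10) = 0.818.
- P(bundle | off target) = 0.05 / (0.05 + 0.40) = 0.111.
- Difference 0.707 (0.652 to 0.767 for 85% to 95% compliance). A 5-point effect of the other bundle content, an assumption, would show as 0.707 × 5 = 3.5 points of apparent rate effect.

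**3. After site adjustment** (linear approximation, equal site sizes, stepped sites crossing midway).
- Within-site covariance of bundle and on-target: zero at the 10 fixed sites; 10 × 0.25 × 0.70 = 1.75 at the stepped sites.
- Within-site variance of on-target: 5 × 0.16 + 5 × 0.09 + 10 × 0.2475 = 3.725.
- Ratio 1.75 / 3.725 = 0.47 (0.41 to 0.54 for 85% to 95%); × 5 = 2.3 points.
- Simulations with staggered crossover times (N = 1,200, ICC about 2%, true rate effect zero) give 1.7 to 1.9 points, with about 9% false positives.

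**4. Secular trend alone, after site adjustment.** Assume survival rises 10 points over the trial.
- With midway crossing and time scaled 0 to 1, the covariance of bundle with time is 0.375 − 0.25 = 0.125. With on-target it is 0.70 × 0.125 = 0.0875 per stepped site, 0.875 in all.
- 0.875 / 3.725 = 0.235; × 10 = 2.3 points.
- Staggered crossover in simulation gives about 1.9 to 2 points, with 8% to 11% false positives. A falling trend would reverse the sign.

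**5. Both together, and with the terms added.** In simulation, 5 points plus the 10-point trend gives +3.7 points and 20% false positives. With bundle status and time in the model the estimate returns to about 0, with 5% to 6% false positives. Time alone removes the trend part but not the part due to other bundle content.

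**6. Price of each term.** Adding time widens the standard error by about 4% in simulation. For bundle status, use SE = √(0.35 × 0.65 / (1,200 × v)), where v is the remaining variance of on-target status, and power = Φ(0.10 / SE − 1.96).
- Pooled, v = 0.2475: power 95%.
- Site-adjusted, v = 3.725 / 20 = 0.186: 88%.
- Site plus bundle, v = 0.5 × 0.16 + 0.5 × 0.09 = 0.125: 73%.

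**The case against.** **Detail for the analysis plan.** These are embedded observational aims under a brief description that speaks of controlling for potential confounders, and final covariates are often fixed later. That would answer an omission. But this protocol writes out a list, carries it into the epoch-level models, and claims an unbiased result that the list cannot support.

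**The assumed effects may be too large.** Section 1.1 says survival plateaued nearly ten years ago. Section 1.4 reports that the earlier compression-focused bundle, with over 90% compliance, did not improve outcomes. Section 7.1 says many sites already do bedside arrest preparation, so the teaching contrast may be diluted. This stands as a limit on size. It does not explain why time belongs in the primary model but not here.

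**Conditioning on bundle status has a price.** The bundle is the randomized source of variation in rate. Adjusting for it leaves only within-phase variation, which patient and provider factors may drive more strongly, and precision falls (step 6). This stands, and is why bundle status belongs in a sensitivity fit.

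**Stronger readings that the text does not support.**
- A reader might infer that the bundle trains airway-pressure targets. Section 7.1 reviews current ventilator settings and sets no pressure.
- A reader might infer that the Airway Opening Index analyses are confounded in the same way. They are exploratory, and the survival model there names no covariates. That the bundle may alter airway pressure makes it a cause of the exposure; confounding would need a further path to the index, and none is shown.
- A reader might apply the post-arrest teaching to every model. It cannot affect pressures or exhaled CO2 measured during CPR.
- A reader might see a contradiction between sections 1.2 and 7.1. Section 7.1 elaborates the same two components.

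**Conclusion.** The point holds for the ventilation-rate analyses: rate against survival, and epoch-level rate against diastolic pressure and exhaled CO2. For the epoch-level models the concern is calendar time and the ventilator-settings review; post-arrest teaching bears only on survival outcomes.

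After the planned site adjustment, and with no true rate effect, the apparent effect is about 2 points from an assumed 10-point trend, or about 1.7 to 2.3 points from an assumed 5-point effect of other bundle content, against a 10-point design contrast. The protocol supplies neither assumed effect. The figures also rest on equal site sizes and 90% vs 20% compliance.

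The bias is moderate, and its time component is cheap to remove. The primary bundle-versus-control comparison is not affected.

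**What to change.** In Protocol 6.3:
- Add time since trial start to the adjustment set of the ventilation-rate models, both survival and epoch-level. Cost: one covariate the primary model already uses, and a standard error about 4% wider.
- Report a sensitivity fit that also includes bundle status at the time of arrest. State beside it that power for 30% vs 40% falls to about 73% by linear approximation, and that it uses only within-phase variation in rate.
- Replace the claim that the validation set gives an unbiased estimate of effect. Say that the split removes optimism from selecting the target rate but not confounding, and that the result is an adjusted association.

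No new data collection is needed, and the primary analysis stays as written.
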